EN: Primary estimand for binary endpoint. For week 1, death or any use of escape medication, and, for week 4, death, or any use of escape medication, or OL Spesolimab use at D8, or any rescue medication with Spesolimab, prior to observing the endpoint(s) is considered to represent a non-response.

EN-PC: Alternative estimand for binary endpoint. For week 1, death or any use of escape medication, and, for week 4, death, or any use of escape medication, or OL Spesolimab use at D8, or any rescue medication with Spesolimab, prior to observing the endpoint(s) is considered to represent a non-response. Any data after the use of restricted medication for other purpose will be censored.

OC = observed cases excluding values after any use of escape medication, or OL Spesolimab use at D8, or any rescue medication with Spesolimab, OC-IR = observed cases including also values after any use of escape medication, or OL Spesolimab use at D8, or any rescue medication with Spesolimab.

"NRI", "BRI" and "EM" (Exhaustive method) mean analyses involving imputed data, cf. [Section 6.6.2](#).

Continuous efficacy endpoints for randomized dose at Day 1

For the primary estimand of continuous endpoints, death or any use of escape medication, or OL Spesolimab at Day 8, or any rescue medication with Spesolimab, prior to observing the endpoint(s) is considered to represent a non-response. Here the outcome of "non-response" itself is not a missing value but is the worst possible outcome of the corresponding

continuous endpoint. See [Section 7.5.2](#) for how to display continuous endpoint with both “non-response” outcome and other numeric continuous values.

The primary imputation strategy of missing values of continuous endpoints is LOCF after the implementation of estimand concept:

- Impute the missing outcome as the last available value (including baseline) prior to the missing outcome;

Wilcoxon rank test on secondary continuous endpoints:

For secondary continuous endpoints, a rank-based approach will be used for testing as below:

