		Patient has rescue medication with Spesolimab x days from randomized treatment., and has no escape medication prior to endpoint collection at Week 4 (independent of whether OL Spesolimab was administered at D8 or not)	106-x/1000 for Pain VAS 22-x/1000 for PSS -58+x/1000 for FACIT-Fatigue scale PT4+6-x/1000 for percentage change from baseline in GPPASI at Week 4
		Patient has escape medication y days after randomized treatment and prior to endpoint collection at Week 1/4 ¹ (independent of whether OL Spesolimab was administered at D8 or not, or rescue medication was taken)	108-y/1000 for Pain VAS 24-y/1000 for PSS -60+y/1000 for FACIT-Fatigue scale PT1/4+8-y/1000 for percentage change from baseline in GPPASI at Week 1/4

Table 6.6.2: 2 Ranking rules for Wilcoxon rank tests of secondary continuous endpoint on EN (cont'd.)

	Category	Ranking	Case description	Imputed change from baseline for further ranking score*
3	Patient died before the measurement at Week 1/4 ¹	Ranked by time to death from randomized treatment.	Patient died z days after randomized treatment. (independent of the occurrence of other events)	110- z /1000 for Pain VAS 26- z /1000 for PSS -62+ z /1000 for FACIT-Fatigue scale PT1/4+10- z /1000 for percentage change from baseline in GPPASI at Week 1/4

* Ranked values in this table are only for purpose of rank tests but not for any descriptive displays

¹ For percentage change from baseline in GPPASI at week 1, the imputation rule is based on the data at week 1, but for other secondary continuous endpoints, it is based on the data at week 4.

Other sensitivity analysis of continuous endpoints include an additional estimand (EC) whereby any data after use of escape medication/OL Spesolimab at D8/rescue treatment with Spesolimab will be censored. The following two methods may be used to handle the censored or missing data here:

- A mixed effect model for repeated measurements (MMRM) will be used to handle the missing cases implicitly.
- (For secondary continuous endpoints only) LOCF method will be used to impute the missing cases.

In addition, OC and OC-IR methods will be implemented to display the data descriptively if needed.

With regard to the handling of missing data on the secondary continuous efficacy endpoints at Week 4, which are included in the testing strategy, the following table gives an overview of the proposed estimand implementation and missing data imputation methods which are planned to be used.

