All days are counted relative to the day of randomized treatment, which is defined as Day 1.

^A Note that measurements made at Day 1 and assigned to the on-treatment period (because mistakenly made after start of trial treatment) via assessment on date & time (i.e. safety laboratory) will not be assigned to Day 1. Such data will be listed only.

^B Since visits 5-8 are optional, the assessments (if any) will not be displayed in tables or figures only if otherwise specified.

^C Patients who receive rescue treatment with OL Spesolimab between Wk7-Wk12 will not have scheduled V14, however if there is any unscheduled assessment between the defined extended time window for V14, it will be still used.

^D All tables and figures by visit will only report visits up to week 12 (if applicable). “Post Week 12” and “off treatment” won’t be used for any tables or figures.

^E For primary analysis visit (V9), only the assessments prior any non-randomized treatment will be used except for those pre-specified post-treatment assessments.

Repeated and unscheduled efficacy, safety and other measurements will be handled similarly to scheduled measurements and will also be assigned to a time window depending upon the date of measurement.

Notice that for EN, EN-PC and EN-ID8 estimands, any observation post intercurrent events of interests (i.e., death, escape medication or rescue medication with Spesolimab for all 3 estimands or OL Spesolimab at D8 for EN and EN-PC only) will be set to be “non-response”. Further, within the extended time window of a visit, if the day of the intercurrent event is prior to the date of planned visit, then a “non-response” observation will be assigned to that day. If the day of the intercurrent event is on or after the date of planned visit, then a “non-response” observation will be assigned to that day only if there is no other observation on the same day, otherwise, no additional observation will be assigned.

Only one observation per time window will be selected for statistical analysis at a particular visit – the value which is closest to the protocol planned visit day will be selected. If there are two observations which have the same difference in days to the planned day, but which are not measured on the same day, the later value will be selected. If there are two observations on the same day, the worst value will be selected.

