7.4 PRIMARY ENDPOINT

The evaluation of patients achieving a GPPGA pustulation subscore of 0 at Week 1 is the primary endpoint of this trial.

Death, or any use of escape medication prior to observing the primary endpoint(s) is considered to reflect a failure to achieve the endpoint outcome, i.e. non-response. In this concept, death, or any use of escape medication after the actual assessment time point of week 1 is not considered. If time is not collected, death or any use of escape medication on or after the actual assessment day of Week 1 is not considered.

The Suissa-Shuster Z-pooled test, will be implemented to test the treatment effect on the primary endpoint on the RS (estimand EN), at a 1-sided, alpha level of 0.025. Confirmation of efficacy is then given only if the null hypothesis on the primary endpoint is rejected. In the output, the result will be reported at 2-sided alpha level of 0.05 which is more common way in CTR but it is exactly same as 1-sided alpha level of 0.025. Confidence intervals (95%) around the risk difference will be produced using the Chan and Zhang method ([6](#)).

Example SAS code for Suissa-Shuster Z-pooled test is as follows:

```
PROC FREQ DATA=data;
  TABLES treat*endpoint_bin;
  EXACT BARNARD (column=2);
RUN;
```

Example SAS code for CI of proportion difference by Chan and Zhang method is as follows:

```
PROC FREQ DATA=data;
  <WHERE treat IN ('Treatment_1','Treatment_2');>
  TABLES treat*endpoint_bin / RELRISK RISKDIFF;
  EXACT RELRISK (METHOD=SCORE column=2) RISKDIFF (METHOD=SCORE
  column=2);
RUN;
```

Graphical displays (Line plots) of the response on primary endpoint will be produced over time (with 95% confidence intervals based on the Wilson score) up to, and including, Visit 14 (Week 12).

Secondary analysis for the primary endpoint will include:

- A sensitivity analysis utilizing the PPS;
- Sensitivity analyses on the RS which utilize alternative methods for the handling of missing data as described in [Section 6.6.2](#).
- Analysis of an additional estimand (EN-PC) whereby death or any use of escape medication, prior to observing the week 1 primary endpoint will be considered to

represent a non-response. For patients who use restricted medication for other purpose prior to Week 1, data will be censored for further analysis following the restricted medication use and imputed using NRI method as described in [Section 6.6.2](#).

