7.5.2 Secondary endpoints

Secondary endpoints included in the testing procedure

The treatment effect on the following secondary endpoint will be tested in a hierarchical manner as a part of the pre-specified testing strategy (see Section 7.2 of the CTP), subsequent to the test of the primary endpoint and key secondary endpoint:

- 1) The proportion of patients achieving a GPPASI 75 at Week 4,
- 2) The change from baseline in pain VAS score at week 4,
- 3) The change from baseline in PSS score at week 4, and,
- 4) The change from baseline in the total FACIT-Fatigue score at Week 4.

GPPASI 75 at Week 4

The primary analysis for the proportion of patients achieving a GPPASI 75 at Week 4 will be performed using the same approach as that defined for the primary analysis of the primary endpoint, based on the RS (estimand EN).

Graphical displays will be produced using the same method as described for the primary endpoint.

Sensitivity analysis for GPPASI 75 at Week 4 will include:

- Sensitivity analyses on the RS which utilize BRI respectively for the handling of missing data as described in [Section 6.6.2](#).

Descriptive subgroup displays (via estimand EN) will be done for the applicable subgroups as defined in [Section 6.4](#) using the RS.

Pain VAS score, PSS score, and FACIT-Fatigue score at Week 4

For the analysis of each of the continuous secondary endpoints which are included in the statistical testing strategy, the following approach will be done:

Any assessments after death, or the use of escape medication, or OL Spesolimab at D8, or rescue medication with Spesolimab, will be considered as “non-response” and assigned with worst outcome for the analysis (estimand EN). In this concept, death, or any use of escape medication or OL Spesolimab at Day 8 or of rescue medication with Spesolimab after the actual endpoint assessment time point at week 4 is not considered. If time is not collected, death, or any use of escape medication or of rescue medication with Spesolimab on or after the actual assessment day of Week 4 is not considered.

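### SAP 6.7 can overwrite a valid Week 4 assessment made on Day 26–28 with non-response when escape medication first starts on Day 29–32 and no assessment is made that day, contrary to SAP 7.5.2

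*SAP*

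**What the plan says.** SAP Table 6.7:1 plans Week 4 for Day 29, with a protocol window of ±3 days (Day 26–32) and an extended analysis window of Day 26–43. SAP 6.7 applies the estimand before it assigns visits, in three steps.

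- **Post-event values.** Under EN, "any observation post intercurrent events of interests" is set to non-response.
- **Added record.** For an event inside the window and on or after the planned visit date, a non-response "observation will be assigned to that day only if there is no other observation on the same day".
- **Selection.** Of the records in the window, "the value which is closest to the protocol planned visit day will be selected"; equal distances on different days go to the later one.

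Other parts of the SAP say which events count:

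- SAP 7.5.2, for Pain VAS, PSS and FACIT-Fatigue: an event "after the actual endpoint assessment time point at week 4 is not considered". If time is not collected, escape on the assessment day is disregarded as well.
- The EN definition in SAP 6.6.2: an event "prior to observing the endpoint(s) is considered to represent a non-response".
- The escape row of SAP Table 6.6.2:2: "escape medication y days after randomized treatment and prior to endpoint collection".
- GPPASI 75 has no such sentence of its own. SAP 7.5.2 has it "performed using the same approach as that defined for the primary analysis of the primary endpoint", and the sentence reached that way, in SAP 7.4, is about Week 1: "any use of escape medication after the actual assessment time point of week 1 is not considered".

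The protocol (2.1.4 and Table 7.5:1) counts escape use before Week 4, and its Flow Chart puts the end of Week 4 at Day 29.

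**The concern.** SAP 6.7 compares distances from Day 29. It never compares the date of the event with the date of the assessment. A patient seen on Day 26, within the protocol window, who first needs escape medication on Day 30 has a real value at distance 3 and an artificial non-response at distance 1. SAP 6.7 takes the artificial one, while SAP 7.5.2 keeps the real one.

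The four Week 4 endpoints in the testing hierarchy depend on these rules, and GPPASI 75 gates the other three. Two programmers working from different sections could classify the same patient differently. Settling the matter after unblinding would be a data-dependent choice inside the hierarchy.

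**Working it through.** The documents give no figure for this rule, so there is none to reproduce. As a check on the test calculation, the exact one-sided Z-pooled test at 34:17 gives 96.28% power at 0.6 v 0.1, against 96.3% in protocol Table 7.7:1.

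**1. Which days conflict.** An assessment on day *a* (26–32) is displaced by escape on day *e* ≥ 29, with *e* after *a* and no same-day observation, if |*e* − 29| ≤ |*a* − 29|. Equality counts because ties go to the later day.

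| Assessment | Distance from Day 29 | Escape days that displace it | Pairs |
|---|---|---|---|
| Day 26 | 3 | 29, 30, 31, 32 | 4 |
| Day 27 | 2 | 29, 30, 31 | 3 |
| Day 28 | 1 | 29, 30 | 2 |
| Day 29–32 | 0–3 | none | 0 |

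The total is 9 pairs, whether the planned visit date in SAP 6.7 is read as Day 29 or as the patient's actual visit date. Under SAP 7.5.2 none of the nine becomes non-response.

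**2. Second route.** Withholding the added record is not enough. A later assessment, itself set to non-response because it follows escape, can still be as close to Day 29 or closer. An example is visit Day 26, escape Day 30, unscheduled assessment Day 31. This can happen in 6 of the 9 pairs: 26/29, 26/30, 26/31, 27/29, 27/30 and 28/29.

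**3. Week 1.** The planned day is Day 8 and the window is Day 8–10. No in-window assessment precedes the planned day, so no later event can be closer. There are no affected pairs.

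**4. How many patients.** The documents give no escape rate. Assume a fraction *r* of *n* patients first use escape uniformly over Day 15–43 (29 days), visits are uniform over Day 26–32 (7 days), and there is never a same-day assessment. Then the expected number is *n* × 9 × (*r*/29) × (1/7).

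- *n* = 34: *r* = 2%, 10%, 20% gives 0.03, 0.15, 0.30. At 10%, P(at least one) = 0.140; at 20%, 0.261.
- *n* = 51, *r* = 10%: 0.23, P = 0.203.
- *n* = 24 still event-free, half of escape starts with a same-day assessment, *r* = 10%: 24 × 9 × (0.10/29) × (1/7) × 0.5 = 0.05, P = 0.052.

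**5. GPPASI 75.** One lost spesolimab responder matters only on the boundary of significance. For example, 14/34 v 2/17 has one-sided p = 0.0215 and 13/34 v 2/17 has p = 0.0394. The probability of lying exactly on the boundary is 2.0% at 0.6 v 0.1 (borrowed from the Week 1 planning rates), 8.8% at 0.4 v 0.1 and 10.8% at 0.3 v 0.05. Multiplying by P(at least one), and counting every displaced patient as a lost spesolimab responder:

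- 10% escape, *n* = 34: 0.140 × 0.020 = 0.3%; 0.140 × 0.088 = 1.2%; 0.140 × 0.108 = 1.5%.
- 20% escape, *n* = 34, 0.4 v 0.1: 0.261 × 0.088 = 2.3%.
- 10% escape with the two reductions: 0.052 × 0.020 = 0.1%; 0.052 × 0.088 = 0.5%.

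**6. Continuous endpoints (normal approximation).** SD of U = √(34 × 17 × 52/12) = 50.05. One displaced spesolimab patient changes U by at most 17, so z falls by at most 17/50.05 = 0.34. If 30 of 51 patients share the Day 8 open-label rank, the tie factor is √(1 − 26970/132600) = 0.8925 and the fall is at most 0.34/0.8925 = 0.38. A significant result could then be lost only if its one-sided p was already between about 0.010 and 0.025.

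**The case against.** The best defence is a harmonised reading. SAP 7.5.2 defines EN so that escape after the actual assessment does not count, and SAP 6.7 applies the estimand before visits are assigned. A later escape would then not be an event of interest for that visit, and the added record would serve only patients with no assessment before the event. This is probably what was intended. But SAP 6.7 does not state that qualifier, SAP 7.5.2 does not refer to SAP 6.7, and nothing says which prevails. For GPPASI 75 the protection has to be carried over from a Week 1 sentence. The conflict in the text stands.

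Three points do narrow it.

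- **Same-day assessments.** A same-day observation stops the added record, and protocol 6.2.2.2 allows an unscheduled visit for worsening. It does not require one. Open-label rescue normally has pre-dose assessments that day (Flow Chart footnote 3), so rescue is not claimed here.
- **Blinded data review.** The planning and database lock meetings (SAP 6.2 and 6.3) could catch a case, but they have no rule to apply.
- **Power.** Protocol 7.2 says the study is not further powered for these tests.

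A reader might go further and infer three things that the documents do not support.

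- **That the primary result is at risk.** The Week 1 window rules this out.
- **That the rule favours spesolimab.** SAP 7.5.2 expects most placebo patients to have had escape or open-label treatment by Day 8. If so, patients still event-free at Week 4 are mainly on spesolimab and the error mainly costs power. A displaced placebo responder would act the other way.
- **That events on Day 26–28 after an earlier assessment are equally wrong.** These precede Day 29, so the protocol's wording may count them while SAP 7.5.2 does not. That is a separate open question.

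**Conclusion.** The point holds, and it is minor. In nine specific day pairs, and only without an assessment on the escape day, SAP 6.7 as written turns a valid Week 4 value into non-response against three other places in the SAP. The protocol gives the overwrite no support, because escape from Day 29 on is not before Week 4. The day pairs follow directly from the text and need no assumption.

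The size does rest on assumptions: escape rate, uniform timing, no same-day assessments and Week 4 response rates. Zero or one patient is likely. The chance of a changed GPPASI 75 result is about 0.1% to 2.3% over the cases tried. None of these figures is an upper limit: escape clustered just after the visit, or other response rates, could exceed them. Besides the four tested endpoints, the rule reaches the untested Week 4 endpoints. The same mechanism exists in the Week 2, 3, 8 and 12 windows that feed the displays over time.

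**What to change.** Before unblinding, add one general rule to SAP 6.7, for every visit window. It applies where the patient's actual assessment for the visit was made before the intercurrent event (or on the same day, if time is not collected) and the event falls on or after the protocol planned day. In that case:

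1. no non-response record is added for that visit; and
2. later observations set to non-response because of that event are not candidates for that visit.

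The second part is needed for the six pairs in step 2 of the working. State that the rule covers all Week 4 endpoints under EN, including GPPASI 75. The added record stays for patients with no assessment before the event.

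Separately, for events on Day 26–28 after an earlier in-window assessment, the sponsor should reconcile the protocol's cut-off at Week 4 with the SAP's cut-off at the actual assessment and state the result.

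The cost is one or two sentences in the SAP and one programming condition. No new data are needed.

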7. PLANNED ANALYSIS

Primary analysis of study will be performed once all patients have completed 12 weeks study period or early discontinue. A snapshot will be taken for the primary analysis and all patients' data up to the cut-off date will be included into analysis.

Final trial analysis is planned to be performed at the end of the study once all randomized patients have completed the study (including any follow-up period) if applicable. Additional but limited data after primary analysis snapshot will be listed in final analysis.

A database lock for the primary analysis will be done and treatment will be un-blinded. In order to warrant the integrity of the treatment blind while the trial continues through completion, a logistics plan will be developed to describe the mechanisms that are to be put in place to assure that the patients and investigators remain blinded to both individual patient data, as well as the primary analysis results. The blind status of trial and project team members at this time will also be clarified. The logistics plan will be finalized prior to the treatment un-blind for the primary analysis.

The primary analysis and final analysis may be performed as a single analysis (at the time of trial completion), if, prior to the time of the primary analysis, the trial team agrees that the expected time interval between the planned analyses is insufficient to justify the performance of separate analyses.

The format of the listings and tables will follow the BI guideline "Reporting of clinical trials and project summaries" (001-MCG-159) ([10](#)). The individual values of all patients will be listed. Listings will generally be sorted by country, center number, patient number and visit (if visit is applicable in the respective listing). AE listings will be sorted by assigned treatment (see [Section 7.8.1](#) below for details). The listings will be contained in Appendix 16.2 (SDL) of the CTR.

The following standard descriptive statistical parameters will be displayed in summary tables of continuous variables:

N	number of non-missing observations
Mean	arithmetic mean
SD	standard deviation
Min	minimum
Q1	lower quartile
Median	median
Q3	upper quartile
Max	maximum

Statistical parameters will be displayed to a defined number of decimal places as specified in the BI guideline "Reporting of clinical trials and project summaries" ([10](#)).

Tabulations of frequencies for categorical data will include all possible categories and will display the number of observations in a category as well as the percentage (%) relative to the

respective treatment. Percentages will be rounded to one decimal place. The category missing will be displayed if and only if there actually are missing values. Percentages will be based on all patients in the respective patient set whether they have non-missing values or not.

Disposition of the patient population participating in the trial will be summarized by the presentation of the frequency of patients screened, randomized, screened but not randomized, randomized but not treated, randomized and treated, who completed trial medication (on Day 1), who were prematurely discontinued from trial medication (on Day 1), by reason, who completed participation in the trial, who were prematurely discontinued from trial, by reason, and who entered the extension trial 1368.25.

The frequency of patients with iPDS, also summarized by whether or not the iPD led to exclusion from the PPS, will be presented. The frequency of patients in each of the different analysis sets will also be presented.

